14.4 Primary Adverse events

The Primary Adverse Events of interest include the following:

 Death
 Atria-Esophageal Fistula*
 Cardiac Tamponade/Perforation
 Myocardial Infarction
 Stroke/Cerebrovascular Accident
 Thromboembolism
 Transient Ischemic Attack
 Diaphragmatic Paralysis
 Pneumothorax
 Heart Block
 Pulmonary Vein Stenosis
 Pulmonary Edema (Respiratory Insufficiency)
 Pericarditis
 Major Vascular Access Complication/Bleeding

Table 14.4: Primary Adverse Events are defined as following:

PRIMARY ADVERSE EVENT	DESCRIPTION / CRITERIA
Death	Subject death directly related to the device or procedure and occurs at any time during or after the procedure.

PRIMARY ADVERSE EVENT	DESCRIPTION / CRITERIA
Atrio-Esophageal Fistula*	Is defined as a connection between the atrium and the lumen of the esophagus. Evidence supporting this diagnosis includes documentation of esophagus erosion combined with evidence of a fistulous connection to the atrium such as air emboli, an embolic event, or direct observation at the time of surgical repair. A CT or MRI scan is the most common method of documentation of an atrio-esophageal fistula.
Cardiac Tamponade**/Perforation	The development of a significant pericardial effusion during or within 30 days of undergoing an AF ablation procedure. A significant pericardial effusion is one which results in hemodynamic compromise, requires elective or urgent pericardiocentesis, or results in a 1 cm or more pericardial effusion as documented by echocardiography. Cardiac tamponade should also be classified as "early" or "late" depending on whether it is diagnosed during or following initial discharge from the hospital.
Myocardial Infarction	The presence of any one of the following criteria: 
 • Detection of ECG changes indicative of new ischemia (new ST-T changes or new LBBB) which persists for more than 1 h • Development of a new pathological Q waves on an ECG, and • Imaging evidence of new loss of viable myocardium or new regional wall motion abnormality

PRIMARY ADVERSE EVENT	DESCRIPTION / CRITERIA

Stroke / Cerebrovascular Accident
	
Rapid onset of a focal or global neurological deficit with at least one of the following: change in level of consciousness, hemiplegia, hemiparesis, numbness or sensory loss affecting one side of the body, dysphasia or aphasia, hemianopia, amaurosis fugax, or other neurological signs or symptoms consistent with stroke.
 
Duration of a focal or global neurological deficit ≥ 24 h; or < 24 h, if therapeutic intervention(s) were performed (e.g. thrombolytic therapy or intracranial angioplasty); OR available neuroimaging documents a new hemorrhage or infarct; or the neurological deficit results in death.
 
No other readily identifiable non-stroke cause for the clinical presentation (e.g., brain tumor, trauma, infection, hypoglycemia, peripheral lesion, pharmacological influences)[†]
 
Confirmation of the diagnosis by at least one of the following:
 
 • Neurology or neurosurgical specialist • Neuroimaging procedure (MR or CT scan or cerebral angiography) • Lumbar puncture (i.e., spinal fluid analysis diagnostic of intracranial hemorrhage) 
Stroke: (diagnosis as above, preferably with positive neuroimaging study)
 
 • Minor—Modified Rankin score < 2 at 30 and 90 days^{††} • Major—Modified Rankin score ≥ 2 at 30 and 90 days

PRIMARY ADVERSE EVENT	DESCRIPTION / CRITERIA
Thromboembolism	Formation of a clot (thrombus) inside a blood vessel causing obstruction to blood flow. The thrombus can migrate (embolus) and obstruct distal vascular sites. Diagnostic tests to help detect thromboembolisms may include but are not limited to angiography (pulmonary or distal), ventilation- perfusion (V/Q) scans, venography, Doppler ultrasonography, spiral CT, and echocardiography.
Transient Ischemic Attack	New focal neurological deficit with rapid symptom resolution (usually 1 to 2 h), always within 24h Neuroimaging without tissue injury.
Diaphragmatic Paralysis	Absent phrenic nerve function as assessed by a sniff test. A phrenic nerve paralysis is considered to be permanent when it is documented to be present 12 months or longer following ablation.
Pneumothorax	Introduction of air into the intra-pleural cavity necessitating chest tube placement or surgical intervention.
Heart Block	Impairment of AV conduction requiring intervention (e.g. temporary or permanent pacemaker) due to iatrogenic cause (e.g. inappropriate RF application, traumatic maneuvering of catheter or other intracardiac devices).
Pulmonary Vein Stenosis***	A reduction of the diameter of a PV or PV branch. PV stenosis can be categorized as mild <50%, moderate 50-70%, and severe 70% reduction in the diameter of the PV or PV branch. A severe PV stenosis will be considered a major adverse event and major complication of AF ablation.
Pulmonary Edema (Respiratory Insufficiency)	Respiratory insufficiency resulting in pulmonary complications necessitating intubation or other significant intervention (including diuretics administered specifically for treating pulmonary edema or ICU hospitalization requiring oxygen administration but not intubation) Exclusion criteria include: 
 • Pneumonia – infiltrate, fever and leukocytosis • Acute Respiratory Distress Syndrome
Pericarditis	Should be considered a major complication following ablation if it results in effusion which leads to hemodynamic compromise or requires pericardiocentesis, prolongs hospitalization by more than 48 h, requires hospitalization, or persists for more than 30 days following the ablation procedure.

PRIMARY ADVERSE EVENT	DESCRIPTION / CRITERIA
Major Vascular Access Complication / Bleeding	
Major Bleeding: A major complication of AF ablation if it requires and/or treated with transfusion or results in a 20% or greater fall in HCT.
 
Major Vascular Access Complication: Defined as a hematoma, an AV fistula or a pseudoaneurysm which requires intervention such as surgical repair or transfusion, prolongs the hospital stay, or requires hospital admission.

* Pulmonary vein (PV) stenosis and atrio-esophageal fistula that occurs greater than one week (7 days)

post-procedure shall be deemed Primary AEs.

** Hemodynamic compromise or instability is defined as Systolic BP < 80 mm Hg.

† Subjects with non-focal global encephalopathy will not be reported as a stroke without unequivocal evidence based upon neuroimaging studies.

†† Modified Rankin score assessments should be made by qualified individuals according to a certification process. If there is discordance between the 30 and 90 day Modified Rankin scores, a final determination of major versus minor stroke will be adjudicated by the neurology members of the clinical events committee.

14.5 Anticipated Adverse Events

An anticipated Adverse Event is an effect which by nature, incidence, severity or outcome has been identified as possible complications associated with the investigational medical device and/or intervention procedure.

Potential adverse events that are reasonably anticipated to occur during the cardiac electrophysiology procedure include all of the events noted in any clinical study for these types of Radiofrequency RF devices to date are listed in Table 14.5.

Anticipated Adverse Events	
1.	Acute Respiratory Distress Syndrome (ARDS)
2.	Air embolism
3.	Allergic reaction / anaphylactic shock
4.	Anemia
5.	Anesthesia reaction (e.g., hair loss)
6.	Apnea - sedation induced
7.	Arrhythmias: bradycardia, tachycardia, pro-arrhythmias, ventricular tachyarrhythmia / pro-arrhythmia
8.	Aspiration pneumonia
9.	Asthmatic attack

Anticipated Adverse Events	
10.	Atelectasis
11.	Atrial fibrillation or other arrhythmia: exacerbation of pre-existing arrhythmia
12.	Atrio-Esophageal fistula
13.	Atypical left atrial flutter
14.	AV fistula
15.	Bleeding complications
16.	Bleeding requiring transfusion
17.	Cardiac arrest
18.	Cardiac perforation / Tamponade
19.	Cardiac thrombo-embolism
20.	Cerebro-vascular accident (CVA) / stroke
21.	Chest pain/discomfort
22.	Complete heart block, temporary or permanent
23.	Conduction block: ongoing / resolved
24.	Congestive Heart Failure
25.	Coronary artery dissection
26.	Coronary artery occlusion
27.	Coronary artery spasm
28.	Coronary artery Thrombosis
29.	Death
30.	Deep venous thrombosis
31.	Dislodgement of ICD (Implantable Cardioverter Defibrillator) or permanent pacing leads
32.	Disseminated Intravascular Coagulation
33.	Dyspnea
34.	Endocarditis
35.	Epistaxis
36.	Esophageal injury
37.	Expressive aphasia
38.	Fainting
39.	Fatigue
40.	Gastro-intestinal disorders like gastric reflux, nausea
41.	Gastrointestinal diverticulosis
42.	Heart Failure
43.	Hematoma (local) /ecchymosis
44.	Hemorrhage
45.	Hemothorax
46.	High / increased creatinine phosphokinase (CPK)
47.	Hypotension

Anticipated Adverse Events	
48.	Hypoxia
49.	Implantable cardioverter-defibrillator (ICD) lead malfunction
50.	Increased phosphokinase level
51.	Infection, localized or systemic
52.	Laceration
53.	Leakage of air or blood into the lungs or other organs due to perforation
54.	Liver toxicity
55.	Mobile strands in Inferior Vena Cava
56.	Myocardial Infarction
57.	Neurological disorders (tremor, poor coordination, headache, ...)
58.	Obstruction / perforation / damage to the vascular system
59.	Parkinson's disease
60.	Pericardial effusion resulting in tamponade
61.	Pericardial effusion without tamponade
62.	Pericarditis
63.	Peripheral embolus
64.	Peripheral nerve injury
65.	Peripheral thromboembolism
66.	Phlebitis
67.	Phrenic nerve damage / diaphragmatic paralysis
68.	Pleural effusion
69.	Pneumonia
70.	Pneumothorax
71.	Pseudoaneurysm
72.	Pulmonary edema
73.	Pulmonary edema / Heart failure
74.	Pulmonary embolism
75.	Pulmonary hypertension
76.	Pulmonary toxicity, like acute pulmonary syndrome
77.	Pulmonary vein dissection
78.	Pulmonary vein Stenosis
79.	Pulmonary vein thrombus
80.	Pump failure
81.	Renal failure
82.	Respiratory depression/failure
83.	Retroperitoneal hematoma
84.	Rhabdomyolysis, including produced by body position or propofol
85.	Sedation induced CO2 retention with lethargy and cholecystitis

Anticipated Adverse Events	
86.	Seizure
87.	Sepsis
88.	Skin burns (due to cardioversion, tape, etc.)
89.	Skin discoloration
90.	Skin injury / muscle or connective tissue injury due to body position, electrical cardioversion
91.	Skin rash
92.	Thrombocytopenia
93.	Thromboembolism
94.	Thrombosis
95.	Thyroid disorders
96.	Transient extremity numbness
97.	Transient ischemic attack (TIA)
98.	Unintended complete or incomplete AV, Sinus node, or other heart block or damage
99.	Urinary retention
100.	Urinary tract infection
101.	Urinary tract injury or infection related to the urinary catheter
102.	Valvular damage/insufficiency
103.	Vasovagal reactions
104.	Vision change
105.	Volume overload
106.	Worsening obstructive, restrictive, or other form of pulmonary disease
107.	X-ray radiation injury of skin, muscle and/or organ

Adverse Device Effect (ADE's) are adverse events related to the use of an investigational medical device. This definition includes adverse events resulting from insufficient or inadequate instructions for use deployment, implantation, installation, or operation, or any malfunction of the investigational medical device. This definition includes any event resulting from use errors or from intentional misuse of the investigational medical device.

Serious Adverse Device Effects (SADE): adverse device effects that has resulted in any of the consequences characteristic of a serious adverse event.

Unanticipated Serious Adverse Device Effect (USADE): Unanticipated serious adverse device effect (USADE) is a serious adverse device effect which by its nature, incidence, severity or outcome has not been identified in the Investigators Brochure or Instruction For Use.

Device Deficiency: Inadequacy of an investigational medical device related to its identity, quality, durability, reliability, safety or performance, such as malfunction (failure of a medical device to perform in accordance with its intended purpose when used in accordance with the instructions for use or protocol), misuse or user error and inadequate labeling.

If a **device deficiency** occurs, especially that could have led to a SAE, the investigator must report the event as per MEDDEV and to the sponsor by completing the event within 24hours after awareness into the eCRF.

If a device deficiency is detected or suspected, it should be documented on the appropriate eCRF and the device must be returned according to the Sponsor's instructions.

If the device deficiency is associated with any SAE (SADE/ USADE) or if a device deficiency occurs that could have led to a SADE if suitable action had not been taken or, intervention had not been made or, if circumstances had been less fortunate or a new findings/updates in relation to already reported events, the investigator must report the event and device deficiency within 24 hours of awareness to the Sponsor.

The sponsor will review all reported device deficiencies and will determine and document in writing whether they could have led to a SADE and report accordingly to the competent and regulatory authorities, and REB/IRB/EC requirements. In case of disagreement between the sponsor and the principal investigator(s), the sponsor shall communicate both opinions to the concerned parties.

Event reporting to relevant competent authorities in accordance with the jurisdictional regulations will occur by the sponsor and/or by the investigator, depending upon the local requirements and will be done in EU per MEDDEV 2.12/1 guidelines for CE-marked devices manufactured by Biosense Webster and per MEDDEV 2.7/3 guidelines for non CE-marked devices manufactured by Biosense Webster. Device Deficiency of concomitant CE marked devices

If a device deficiency of a CE marked device manufactured or distributed by the sponsor and registered locally has occurred, the event has to be notified immediately to the sponsor via Biosense Webster regular complaints handling process and procedures.

In Europe, if this event is considered as an incident according to the definition given in the MEDDEV 2.12/1 guidelines, the sponsor will notify the incidents to the competent authorities or local regulatory authorities, according to the regulatory requirements and company procedures applicable for CE marked medical devices.

Documentation/Follow-up Reporting

All AE/SAE must be monitored until they are adequately resolved or explained, including submission of follow-up reports to the sponsor or designee as soon as the information becomes available. Additional documentation may be requested by the Sponsor or designee, including but not limited to, a written subject narrative detailing the clinical course of the AE/incident, a copy of any correspondence with the local REB/IRB/EC, hospital records, death certificate, and an autopsy report, if available.

Reporting Requirements to Sponsor and Regulatory/ Competent Authorities

All serious AE (SAE/SADE), whether or not they are related to the device or procedure, and Unanticipated Serious Adverse Device Effect (USADE) must be reported to the Sponsor or designee and entered into the eCRF within 24-hours of awareness by the clinical investigation site personnel.

15 STATISTICAL CONSIDERATIONS

15.1 Sample Size

This is a feasibility study of safety and effectiveness in which the sample size of the clinical investigation is intended to provide preliminary estimates of these 2 aspects. Enrollment in the clinical investigation will be approximately 40-70 evaluable subjects.

15.2 Analysis Populations

The following analyses populations will be used to complete the analyses of the data:

Safety Subject Population: The safety subject population will include all enrolled subjects who have the RHYTHMFINDER™ 192 Catheter inserted, regardless if cartofinder guided ablation was performed

Evaluable Subject Population: The evaluable subject population will include all enrolled subjects who have the RHYTHMFINDER™ 192 Catheter inserted and where cartofinder guided ablation was performed

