4 CLINICAL INVESTIGATION OUTCOME MEASURES

4.1 Study Endpoints

Effectiveness

- Acute success defined as: Rate of conversion of Atrial Fibrillation to Normal Sinus Rhythm or Atrial Tachycardia, after CFGA and PVI (without cardioversion)
- Procedural success defined as: Conversion of Atrial Fibrillation to Normal Sinus Rhythm or Atrial Tachycardia after overall ablation procedure, with or without the need for cardioversion
- Rate of conversion of Atrial Fibrillation to Normal Sinus Rhythm or Atrial Tachycardia, after CFGA only (before PVI and without cardioversion)
- Freedom from documented symptomatic AF/AT/AFL recurrence (episodes \geq 30 seconds on an arrhythmia monitoring device) post the 3-month blanking period through the 12-month follow up.
- Incidence of PVI (confirmed entrance block) after adenosine/isoproterenol challenge
- Change of intra-cycle length from pre-CFGA to post-CFGA and post-PVI

Safety

- Incidence of early-onset Primary Adverse Events (refer to section 14 for a list of events).
- Incidence of study device and procedural related SAEs during follow-up period (12M)
- Incidence of all SAEs during follow-up period (12M)
- Incidence of study device and procedure related adverse events

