6.3.1 Baseline Mapping Sequence

All eligible subjects will undergo the CARTOFINDER™ Mapping Procedure, using the RF-192 catheter. The subject must be in AF prior to the insertion of the RF-192 Mapping catheter. If the subject is not in AF at the time of the procedure the patient will be regarded as discontinued per inclusion criteria, followed for 7-days post-procedure and exited from the study.

- Standard Fast Anatomic Mapping (FAM) procedure of the Right Atria (RA) using the THERMOCOOL SMARTTOUCH™ or SMARTTOUCH® SF Catheter.
- Baseline CARTOFINDER™ map, recording of the RA using the RF-192 catheter
 - On deployment of the RF-192 catheter, the basket catheter will be placed in optimal position to maximize contact with the RA wall
 - Once the catheter's position is confirmed and contact is optimal, the investigator will obtain intra-cardiac signals
 - One 30 second recording will be obtained

DO NOT perform any RA ablations at this point

- Transseptal Puncture
- Standard FAM of the Left Atria (LA) using the THERMOCOOL® SMARTTOUCH™ or SMARTTOUCH® SF Catheter.
- Baseline CARTOFINDER™ map, recording of the LA using the RF-192 catheter
 - On deployment of the RF-192 catheter, the basket catheter will be placed in optimal position to maximize contact with the LA wall
 - Once the catheter's position is confirmed and contact is optimal, the investigatorinvestigator will obtain intra-cardiac signals
 - One 30 second recording will be obtained

RF192 catheter must not remain in the subject (being deployed in the atrium) for cumulative duration greater than 1.5 hours (90 mins)

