8 CONCOMITANT THERAPY

The following medications may be administered (as indicated and per standard of care and per the IFU) for subjects undergoing catheter ablation.

Before Ablation:

- Anticoagulation: therapy is recommended for 30 days before the ablation procedure.
- Anti-Arrhythmic Drug (AAD): subjects AAD therapy should be managed per the institutions/investigator's standard of care.

An intravenous bolus of Heparin should be administered before introducing RF-192.

Mapping Procedure: While the RF-192 catheter is in the subject's right atrium, the ACT must be maintained at ≥ 300 ; while placed in the left atrium, the ACT must be maintained at ≥ 350 . When the RF-192 catheter is not in the subject's atrium e.g. in between mapping procedures, the ACTs may be reduced, but must remain at ≥ 300 while the catheter is inside the subject.

Ablation Procedure: Maintain an ACT greater than 300 seconds for right-sided procedures and above 350 seconds for left-sided procedures as in accordance with the current ACC/AHA/ESE guidelines. Post ablation pacing procedure(s) and/or infusion of cardiac medications to induce AF are at the discretion of the investigator (e.g., Isoproterenol 2 to 20 mcg/min).

Following Ablation:

- Anticoagulation therapy is strongly recommended for 3 months following ablation. Thereafter, subjects are recommended to receive anti-coagulation therapy in accordance with the ACC/AHA/HRS 2014 Guidelines for the Management of Patients in Atrial Fibrillation [2, 15]
- At the discretion of the investigator, a previously ineffective drug, at the same dose or lower, may be continued during the 3-month blanking period. Subsequent use of anti-arrhythmic drugs is discouraged
- Additional medications needed to treat clinical indications are at the discretion of the clinical investigation investigator

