11 SUBJECT DISPOSITION

The following subject groups are defined:

- **Enrolled Subjects:** Subjects who have signed and dated the Informed Consent Form.
- **Excluded Subjects:** Enrolled subjects who have signed an ICF but are found not meeting eligibility criteria prior to insertion of the RHYTHMFINDER™ 192 Catheter.
- **Mapping Failure:** Enrolled subjects who have the RHYTHMFINDER™ 192 Catheter inserted and where inability to record baseline CF mapping signals is observed, will be followed up for 7-days.

If an SAE is reported for a mapping failure subject, they will be followed until event resolution or stabilized. The investigator will document mapping failures in the electronic CRF, including reasons for failure.

- **Discontinued Subjects:** Enrolled subjects who have the RHYTHMFINDER™ 192 Catheter inserted but do not undergo CF guided ablation. If subject's arrhythmia is determined at the time of EP study to be a non-study arrhythmia (required for subject enrollment per study inclusion criteria), the subject will be categorized as discontinued subject. Discontinued subjects will remain in follow-up for 7-days. If an SAE is reported for a discontinued subject, they will be followed until event resolution or stabilized.
- **Lost to Follow-up Subjects:** Subjects who are enrolled and have the RHYTHMFINDER™ 192 Catheter inserted, but contact is lost after most recent follow-up visit (despite 3 documented attempts to contact the subject).
- **Withdrawn / Early Termination Subjects:** Subjects who have RHYTHMFINDER™ 192 Catheter inserted but withdraw consent for study participation or are withdrawn by the investigator or are terminated from the study prior to completion of all follow-up visits
- **Completed Subjects:** enrolled subjects who complete the last scheduled follow-up visit per study protocol.

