15.3.1 Safety

Acute safety outcome will be reported as the number of primary adverse events and the number of subjects experiencing primary adverse events (within 7 days of procedure, with exception for PV stenosis and AE fistula (Table 14.4).

Incidence of (S)AEs during follow-up will be reported as the number of (S)AEs and the number of subjects experiencing (S)AEs. The number and percentage of subjects with (S)AEs will be summarized overall and by AE type, seriousness, severity, causality, anticipated or not and outcome. Listing of (S)AEs will also be provided.

The safety population (SP) will be used as the analysis population.

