5.2 Other Endpoints

- Investigational Device Performance
 - Number of identified CF ablation targets
 - Max number of active RF 192 electrodes during initial mapping procedure
- AAD use post the 3-month blanking period
- Incidence of repeat ablation procedures for AF post the 3-month blanking period
- Procedural data
 - All target sites for RF lesion application
 - Location of ablation targets
 - Number of RF applications per target
 - Total RF duration per application
 - RF ablation parameters (including but not limited to: power, contact force, impedance, flow rate, temperature)
 - Total fluoroscopy time and dose
 - Total procedure, mapping and ablation time

6 Levels of Significance

No formal statistical hypothesis and inferential statistics will be formulated and performed. Two-sided 95% confidence intervals will be constructed for the effectiveness and safety endpoints.

7 Analysis Sets

The following analyses populations will be used to complete the analyses of the data:

- **Safety Subject Population (SP)**: The safety subject population will include all enrolled subjects who have the RHYTHMFINDER™ 192 Catheter inserted, regardless if CARTOFINDER guided ablation was performed.
- **Evaluable Subject Population (EP)**: The evaluable subject population will include all enrolled subjects who have the RHYTHMFINDER™ 192 Catheter inserted and where CARTOFINDER guided ablation was performed.

- **Effectiveness Subject Population (Efp):** The effectiveness subject population will include all Evaluable Subjects who meet the study eligibility criteria. Efp was not included in the protocol but added in the SAP.

8 Sample Size Justification

This is a feasibility study of safety and effectiveness in which the sample size of the clinical investigation is intended to provide preliminary estimates of these two aspects. Enrollment in the clinical investigation will be approximately 40-70 evaluable subjects.

9 Data Monitoring Committee (DMC)

No Data Monitoring Committee will be constituted for the study.

10 Analyses to be Conducted

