10.4 Endpoint Analyses

Descriptive statistics and two-sided 95% confidence intervals will be presented for the effectiveness and safety endpoints. No formal statistical hypothesis and inferential statistics will be formulated and performed. Analyses of all endpoints will be performed in the proposed analysis populations excluding the subjects with missing outcomes.

- **Safety**

The incidence of early-onset Primary Adverse Events is the percentage of patients with at least one primary adverse event with onset on Day 0 through Day 7 except for pulmonary vein (PV) stenosis and atrio-esophageal fistula that could occur greater than one week (7 days) post-procedure . The number of primary adverse events and the number of subjects experiencing primary adverse events will be reported.

Incidence of (S)AEs during the 12 month follow-up will be reported as the number of (S)AEs and the number of subjects experiencing (S)AEs. The number and percentage of subjects with (S)AEs will be summarized overall and by AE type, seriousness, severity, relationship to device and procedure, anticipated or not and outcome. Listing of (S)AEs will also be provided.

The SP will be used as the analysis population.

- **Effectiveness**

Effectiveness outcomes includes

1. **Acute Success**: Rate of conversion of Atrial Fibrillation to Normal Sinus Rhythm or Atrial Tachycardia, after CFGA and PVI (without cardioversion)

2. **Procedural Success**: Conversion of Atrial Fibrillation to Normal Sinus Rhythm or Atrial Tachycardia after overall ablation procedure, with or without the need for cardioversion
3. **Acute Success Post-CFGA**: Rate of conversion of Atrial Fibrillation to Normal Sinus Rhythm or Atrial Tachycardia, after CFGA only (before PVI and without cardioversion)
4. Incidence of confirmed entrance block post-PVI after adenosine/isoproterenol challenge
5. Freedom from documented symptomatic AF/AT/AFL recurrence (episodes \geq 30 seconds on an arrhythmia monitoring device) post the 3-month blanking period through the 12-month follow up.
6. Change of intra-cycle length from pre-CFGA to post-CFGA and post-PVI

The number and percentages of subjects with effectiveness endpoints (#1- #5) and the corresponding two-sided 95% binomial confidence intervals will be presented.

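### A subject whose procedure is stopped by a complication before RF-192 insertion enters no planned safety rate or listing and fits no exit category

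*Protocol*

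**What the plan says.** **Who is counted.** Under Protocol 15.2 the Safety Population (SP) "will include all enrolled subjects who have the RHYTHMFINDER™ 192 Catheter inserted, regardless if cartofinder guided ablation was performed". SAP section 7 sets the same condition, "regardless if CARTOFINDER guided ablation was performed". For the safety analyses Protocol 15.3.1 states "The safety population (SP) will be used as the analysis population", and SAP 10.4 states "The SP will be used as the analysis population". Neither document names a safety summary for all enrolled subjects or for all started procedures.

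**What the endpoints cover.** They are not limited to the device. Protocol 4.1 lists "Incidence of study device and procedural related SAEs during follow-up period (12M"), and also device- and procedure-related adverse events of any seriousness. The primary adverse events in Protocol 14.4 include major vascular access complication or bleeding, and cardiac tamponade or perforation.

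**What precedes the basket.** The sequence in Protocol 6.3.1 opens with "Standard Fast Anatomic Mapping (FAM) procedure of the Right Atria (RA"), done with the ablation catheter. Protocol section 8 adds: "An intravenous bolus of Heparin should be administered before introducing RF-192". Vascular access is not listed as a step, but a catheter map inside the atrium requires it.

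**Disposition.** In Protocol section 11, Excluded subjects are those who "are found not meeting eligibility criteria prior to insertion of the RHYTHMFINDER™ 192 Catheter". Mapping Failure, Discontinued, Lost to Follow-up and Withdrawn each require that RF-192 was inserted. SAP 10.2 repeats these definitions and summarises disposition for everyone enrolled.

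**The concern.** Entry to the SP can depend on the outcome being measured. Suppose an access bleed, a heparin event or an injury during the first anatomical map leads the operator to stop. The basket is then never inserted, and the subject leaves the denominator because of the event. Each subject lost in this way carries an event, so each such loss lowers the reported procedure-related rate.

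The same subject has no exit row. The disposition table would show one more enrolled subject than its exit categories can account for, at the point where a reader would look for procedures stopped early.

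Preliminary estimation of safety is one of the two stated aims of this feasibility study (Protocol 15.1). With 40 to 70 subjects, one event is visible in a rate.

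**Working it through.** No figure in the plan depends on this point, and the 40-70 range has no formula behind it, so there is nothing to reproduce. The check sets the definitions against the order of the procedure and then illustrates the size.

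**Step 1: which early complications are lost.** Recording of adverse events starts at consent (Protocol Table 7.4, note 6). SAP 10.4 counts primary adverse events by onset from Day 0 to Day 7, and SAP 10.1 makes Day 0 the day of initial ablation. The SP is therefore a set of subjects, not a period that starts at insertion.

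- Complication before insertion, basket inserted and ablation done the same day: in the SP, counted.
- Complication before insertion, case stopped, basket never inserted: outside the SP, not counted.

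**Step 2: does an exit category fit the second case?** Take an eligible subject.

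| Category (Protocol 11, SAP 10.2) | Condition | Fits? |
|---|---|---|
| Enrolled | consent signed | yes, but not an exit |
| Excluded | eligibility failure before insertion | no |
| Mapping Failure | basket inserted | no |
| Discontinued | basket inserted | no |
| Lost to Follow-up | basket inserted | no |
| Withdrawn / Early Termination | basket inserted | no |
| Completed | last scheduled visit done | unclear: no last visit is stated for this case |

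**Step 3: a related conflict.** Protocol 6.3.1 requires AF before the basket goes in. It treats a subject who is not in AF as discontinued, with 7 days of follow-up. Section 11 defines Discontinued by insertion, and its definition of Excluded would also cover this subject, with no follow-up stated. The two passages disagree.

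**Step 4: size, with assumed counts.** The documents give no rate of early stops. I assume 0 to 2 such subjects, each with a primary adverse event, and no such event in an SP of 40 or 70. The intervals are exact (Clopper-Pearson), as SAP 10.1 specifies for proportions: lower = Beta⁻¹(0.025; x, n−x+1), upper = Beta⁻¹(0.975; x+1, n−x). For x = 0 the upper limit reduces to 1 − 0.025^(1/n), so 1 − 0.025^(1/40) = 8.8%.

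| Stopped subjects added | SP of 40 | SP of 70 |
|---|---|---|
| 0 | 0/40 = 0% (0 to 8.8) | 0/70 = 0% (0 to 5.1) |
| 1 | 1/41 = 2.4% (0.06 to 12.9) | 1/71 = 1.4% (0.04 to 7.6) |
| 2 | 2/42 = 4.8% (0.6 to 16.2) | 2/72 = 2.8% (0.3 to 9.7) |

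**Step 5: how likely is at least one?** With an assumed chance p per procedure, the probability is 1 − (1 − p)^n.

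| p (assumed) | n = 40 | n = 70 |
|---|---|---|
| 0.2% | 7.7% | 13.1% |
| 0.5% | 18.2% | 29.6% |
| 1% | 33.1% | 50.5% |
| 2% | 55.4% | 75.7% |

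For orientation, Protocol 18.1 puts arterial or venous injury below 1% and anticoagulation haemorrhage below 0.5%. Only part of these would occur before insertion and stop the case. For these two classes the lower rows are the more plausible.

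**The case against.** The strongest defence is that exposure to the investigational device is a coherent denominator. RF-192 is the only investigational item in Europe (Protocol Table 2.3), and the ablation is clinically indicated. Some of the risk before the basket therefore belongs to care the patient would have had anyway. This stands, and it is why the insertion-based SP should remain the main set. It does not explain why endpoints worded to include procedure-related events have no analysis that covers a procedure stopped early.

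The events are also not hidden. They go into the eCRF, serious ones are reported to the sponsor, a safety review committee looks at safety data during enrolment (Protocol 18.2), and an end-of-study page is completed for every enrolled subject (Table 7.4, note 7). That is true of recording and oversight, but it is not a planned result. SAP 10.1 promises listings of critical data in general terms, but the adverse event listing in SAP 10.4 sits under the SP. The table shells are a separate document that I have not seen.

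On disposition, Protocol section 12 allows withdrawal by the investigator for safety concerns without mentioning insertion, and exclusion criterion 9 leaves room for the investigator's opinion. A site might use either. However, section 11 still requires insertion for Withdrawn, and a procedural complication is not an eligibility failure.

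Finally, a wider denominator does not always raise the rate, because it also admits subjects stopped early without an event. With assumed counts, 3/60 = 5.0% becomes 3/63 = 4.8% if three such subjects join. This is correct, and it is a reason to show both denominators.

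**Conclusion.** The gap is real and narrow. It concerns an eligible subject whose case is stopped by a complication before RF-192 insertion. That subject is in no planned safety rate or listing and in no exit category.

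Three stronger readings are tempting, and the documents do not support them:

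- A reader might infer that all complications before insertion go uncounted. They count whenever the subject later receives the basket.
- A reader might infer that right atrial mapping as a whole falls outside. Only the anatomical map with the ablation catheter precedes the basket. The right atrial CARTOFINDER recording uses RF-192, and transseptal puncture is listed after it.
- A reader might infer that such a subject has no status at all. The subject remains Enrolled, and what is missing is an exit category.

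The effect is probably small in number and may be nil. On the assumption of 0 to 2 such subjects and no primary events in the SP, the primary adverse event rate would move from 0% to at most 4.8% with an SP of 40, or 2.8% with an SP of 70. The intervals overlap widely and no hypothesis test depends on them. The case for change is that the omission depends on the outcome and is cheap to remove.

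**What to change.** 1. Keep the SP as defined for the main safety analysis and for device-related events.
2. Add to SAP 7 and 10.4 a supplementary summary and listing of primary and procedure-related (S)AEs for all enrolled subjects in whom the study procedure was started. State what marks the start, for example first venous access. Where no ablation takes place, count Study Day from the procedure date, because SAP 10.1 leaves it undefined for such subjects.
3. Add two disposition rows, with reasons, to Protocol section 11 and SAP 10.2: procedure not started; and procedure started, RF-192 not inserted.
4. Reconcile Protocol 6.3.1 with section 11 on the category and follow-up of a subject found not to be in AF before insertion.

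**Cost.** The adverse event data are already collected from consent, so the analysis needs a procedure-started flag, a fallback rule for Study Day, and one more table and listing. The SAP already adds an analysis set that the protocol lacks, so item 2 can be made there. Items 3 and 4 touch the protocol and need an amendment under Protocol 16.3. The procedure-related rate in the supplementary table may be slightly higher than in the SP.
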